5.5 PREMATURE TERMINATION OR SUSPENSION OF STUDY

This study may be temporarily suspended or prematurely terminated if there is sufficient reasonable cause. Written notification, documenting the reason for study suspension or termination, will be provided by the suspending or terminating party. If the study is prematurely terminated or suspended, the PI will promptly inform the IRB and will provide the reason(s) for the termination or suspension.

Circumstances that may warrant termination or suspension include the above mentioned stopping criteria as well as:

- Determination of unexpected, significant, or unacceptable risk to participants
- Demonstration of efficacy that would warrant stopping
- Insufficient compliance to protocol requirements
- Data that are not sufficiently complete and/or evaluable
- Determination of futility

Study may resume once concerns about safety, protocol compliance, data quality are addressed and satisfy the sponsor, IRB and/or FDA.

6 STUDY AGENT

6.1 STUDY AGENT(S) AND CONTROL DESCRIPTION

6.1.1 ACQUISITION

Unblinded study drug will be shipped from the manufacturer Swedish Orphan Biovitrum (Sobi) directly to the site research pharmacist, after all required regulatory and legal documents have been received by the Sponsor.

Replacement Procedures For Investigational Medicinal Product: Resupply shipments or replacement of study drug will be provided by Sobi after consultation with [name].

6.1.2 FORMULATION, APPEARANCE, PACKAGING, AND LABELING

Formulation, Packaging and Labeling: Kineret® is a recombinant, nonglycosylated form of human interleukin-1 receptor antagonist (IL-1Ra). Kineret® consists of 153 amino acids and has

a molecular weight of 17.3 kilodaltons. It is produced by recombinant DNA technology using an *E coli* bacterial expression system.

Kineret is supplied in single use prefilled glass syringes with 29 gauge needles as a sterile, clear, colorless-to-white, preservative free solution for daily subcutaneous (SC) administration. The solution may contain trace amounts of small, translucent-to-white amorphous proteinaceous particles. Each prefilled glass syringe contains: 0.67 mL (100 mg) of anakinra in a solution (pH 6.5) containing anhydrous citric acid (1.29 mg), disodium EDTA (0.12 mg), polysorbate 80 (0.70 mg), and sodium chloride (5.48 mg) in Water for Injection, USP.

The prefilled syringe contains an outer rigid plastic needle shield attached to an inner needle cover. The syringe or needle shield components are not made with natural rubber latex.

Each syringe will have a label that will contain, at minimum, the protocol number, contents (written as "Kineret®"), applicable regulatory cautions, storage conditions, route of administration, and a space to write in the dispensing date, subject identification number and subject initials.

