4 STUDY DESIGN AND ENDPOINTS

4.1 DESCRIPTION OF THE STUDY DESIGN

This is a phase 2, prospective, randomized, triple-blinded, placebo-controlled study of IL-1RA treatment in patients with acute ACL tear and painful effusions. The study population will include up to 40 participants within 28 days of injury. The study is open to male and female participants who are between the ages of 14 and 40, who have ACL tears. Once enrolled will be randomized into 2 groups (20 subjects per group).

- **Group 1** will receive intra-articular injection of Anakinra (Kineret®, IL-1ra; 150mg) 1-28 days after ACL injury.
- **Group 2** will receive intra-articular injection of saline placebo 1-28 days after ACL injury.

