6.1.3 PRODUCT STORAGE AND STABILITY

The prepared syringes of Kineret or placebo will be stored in a separate, temperature controlled refrigerator at the investigative site.

Kineret® should be stored in the refrigerator at 2° - 8° C (36° - 46°F). **DO NOT FREEZE OR SHAKE.** Protect from light. Kineret® should not be used after the expiration date unless otherwise notified by the Principal Investigator.

The study drug will be sent to the designated research staff at the University of Kentucky.

Once a subject is identified and consented, the study coordinator will utilize the syringe corresponding to the assigned patient ID to administer the study medication. It has been shown by HPLC analyses, that Kineret is stable for at least 4 hours at ambient temperature and in light in 0.9%NaCl and in a plastic culture vial.³⁸

The refrigerator temperature must be monitored by site personnel on a regular basis and must be recorded on a temperature log sheet or recorded electronically. In the event that the refrigerator's temperature goes outside the $2^{\circ} - 8^{\circ} C (36^{\circ} - 46^{\circ}F)$ range, the Sponsor or designee should be contacted immediately at the telephone number provided in the protocol. Only temperature excursions outside of the acceptable range, per the Sponsor's procedures, are reported as protocol deviations.

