6.1.4 PREPARATION

The study drug will be kept in a temperature controlled environment according to the manufacturer's recommendations

Under aseptic clean conditions, a total of 200 mg (1.34 mL) of Kineret® (concentration 100mg/0.67ml) will be injected from 2 sterile original prefilled 100 mg syringes of Kineret into a sterile vial. A sterile graduated 5 mL syringe will then be used to draw 150 mg (1 mL) of Kineret for intraarticular injection into the knee. The medication must be transferred from the original prefilled Kineret syringes as the needles are intended for subcutaneous delivery and are not adequate for intra-articular knee injection. No dilution of the medication will be performed.

For the placebo we will utilize 1 mL of 0.9%NACL sterile saline solution drawn up in the same type of syringe as for the Kineret administration in order to maintain double blinding of the study investigator and patients.

The number of study syringes prepared by the designated research personnel or research pharmacist, per day, will depend on the number of potential enrollees or return patients requiring Kineret® injections that day.

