8.6 SAFETY OVERSIGHT

Monitoring for adverse events will be conducted in real-time by the study investigators and study coordinators. Risks involved with this study are considered greater than minimal risk. For this reason, we will utilize the standing independent Data Safety Monitoring Board (DSMB) as chartered by the Center for Clinical and Translational Science (CCTS). The DSMB will meet semiannually or as needed, and will review subject recruitment, AE's, side effects, laboratory results, dropouts, protocol violations, and inclusion/exclusion criteria. More frequent meetings will take place if side effects or other problems are prevalent.

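### The drug-handling sections do not assure the stated triple blind: syringe preparation is not separated from dosing and adverse-event review, and masking rests on syringe type alone

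*Combined protocol and SAP*

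**What the plan says.** Section 4.1 describes a "randomized, triple-blinded, placebo-controlled study of IL-1RA treatment", and Section 10.2.1 repeats the triple-blind claim. Section 6.1.4 is narrower. Its placebo is 1 mL of saline "drawn up in the same type of syringe as for the Kineret administration in order to maintain double blinding of the study investigator and patients".

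On supply and labelling, Section 6.1.1 has unblinded drug shipped to the site research pharmacist. Section 6.1.2 describes the manufacturer's prefilled glass syringe and closes with "Each syringe will have a label that will contain, at minimum, the protocol number, contents (written as 'Kineret", with space for a subject number and initials. It describes the solution as clear and colourless to white, and adds: "The solution may contain trace amounts of small, translucent-to-white amorphous proteinaceous particles".

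On handling, Section 6.1.3 says the drug goes to research staff at the university and that "the study coordinator will utilize the syringe corresponding to the assigned patient ID to administer the study medication". Section 6.1.5 gives that task to the investigator. Section 6.1.4 says: "The number of study syringes prepared by the designated research personnel or research pharmacist, per day, will depend on the number of potential enrollees". Section 8.6 says: "Monitoring for adverse events will be conducted in real-time by the study investigators and study coordinators".

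**The concern.** A blind depends on someone who knows the assignments having no part in dosing or assessment, and on a dispensed product that cannot be told apart by label or appearance. The protocol states neither safeguard. As written, a coordinator could draw up active drug for a participant, help to give it and then review that participant's adverse events, all without a protocol deviation.

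What is at stake is judgement and expectation:

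- The primary endpoint (KOOS-Symptoms) and the other KOOS endpoints are self-reported.
- Adverse-event severity and relatedness are clinician judgements (8.2.1, 8.2.2), and relatedness feeds the halting rule in 8.5.
- The principal investigator may approve otherwise prohibited medication, including NSAIDs (7.6), which could affect symptoms.
- Section 10.2.2 marks evaluation of blinding as not applicable, so a failure would leave no trace.

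**Working it through.** No sample-size or error-rate figure is involved. The check sets the sections side by side, with one piece of arithmetic on volume.

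**1. Who touches the drug, and who assesses.**

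| Step | Role named | Section |
|---|---|---|
| Receives drug | research pharmacist | 6.1.1 |
| Receives drug | research staff | 6.1.3 |
| Prepares syringes | research personnel or pharmacist | 6.1.4 |
| Dispenses | pharmacist or other medically qualified staff | 6.1.5 |
| Administers | coordinator | 6.1.3 |
| Administers | investigator | 6.1.5 |
| Monitors adverse events | investigators and coordinators | 8.6 |

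Sections 6.1.1 and 6.1.3 differ on the recipient, and 6.1.3 and 6.1.5 differ on who administers. No section says that the preparer is a separate unblinded person.

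**2. Label.** The label sentence in 6.1.2 follows the description of the prefilled stock. Section 6.1.4 empties two of those syringes into a vial and draws the dose into a 5 mL syringe. On the natural reading, the labelled syringe is not the one injected. The dispensed syringe is described only as matching the patient's ID (6.1.3, 6.1.5), with no statement of what its label shows or that it is the same in both arms.

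**3. Appearance.** The active is given undiluted (6.1.4) and may range from colourless to white with trace particles (6.1.2). The comparator is saline. Section 6.1.9 calls it matching, but the only stated means is the common syringe type. The syringe is attached by hand at the knee (7.2.1), and no sleeve or cover is mentioned.

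**4. Volume.** Volume = dose × 0.67 mL / 100 mg.

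- 200 mg: 200 × 0.67 / 100 = 1.34 mL, as in 6.1.4.
- 150 mg: 150 × 0.67 / 100 = 1.005 mL, which agrees with the 1 mL in 6.1.4.

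Within 6.1.4, then, active and placebo volumes match at 1 mL. The Protocol Summary instead gives 1.5 ml for 150 mg. At the concentration in 6.1.2, 1.5 mL would hold 1.5 × 100 / 0.67 = 223.9 mg. If active followed the Summary and placebo followed 6.1.4, a graduated syringe would show a 0.5 mL difference. The two statements must be reconciled.

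**5. Timing and records.** Section 6.1.4 scales preparation to people who may enrol, and 6.1.3 stores prepared syringes at the site, so preparation before consent is allowed. Section 6.2 keeps used and unused drug in its original boxes with an account per subject, and does not confine these to an unblinded person.

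**6. Allocation list.** Section 10.2.1 gives the sequence to the principal investigator, who also judges expectedness (8.2.3) and assesses adverse events (8.4.1). This is a second route to the assignments. Sealing the list would not close the route through preparation, and fixing preparation would not close this one.

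**The case against.** The strongest reply is that these sections leave safeguards unstated and do not describe a failure. Much of that is right, and three stronger readings should be set aside.

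- **A reader might infer that the injected syringe is marked with the drug name.** The documents do not support this. The label closes the description of stock that is shipped unblinded, and its contents are transferred before injection. Dispensing by patient ID suggests some coding. They are silent on the dispensed label; they do not say that it identifies the arm.
- **A reader might infer that active and saline look different.** The solution is described as clear, the particles only as possible and in trace amounts, and 6.1.4 gives both arms the same syringe type and 1 mL. A visible difference is possible but not stated.
- **A reader might infer that the blind cannot hold.** That does not follow. Seeing a stored syringe before consent reveals the arm only if its label or contents do, or if the observer prepared it.

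The effect on outcomes may also be indirect. KOOS is self-administered, partly online (7.1.1). Biomarker assays and MRI analysis are done at other institutions, and 10.1.1 mentions blinded data analysis. Restricting preparation to a pharmacist is also only one option; a designated unblinded preparer without other duties would serve equally well.

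What the reply does not answer is the role structure. The text expressly permits unseparated research personnel to prepare syringes, and the groups who give the drug also monitor adverse events. Masking by syringe type does nothing about that, nor about any visible difference in contents.

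**Conclusion.** The concern holds in this form: the triple blind is not assured by the drug-handling sections as written. The firmest part is the missing separation between preparation and dosing or adverse-event review, which needs no inference beyond the text. The masking gap rests on the possibility, raised by the protocol's own product description, that active and saline can be told apart. The label point alone is missing detail.

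In reach, the gap covers every study injection, in up to 40 participants (20 per group). Its effect on results cannot be sized from the documents. A reader might set an assumed bias against the 7.2 points in Section 10.1.1, but that figure is the minimal detectable change cited for KOOS Quality of Life, while the primary endpoint is KOOS-Symptoms. Neither the bias nor the share of participants unmasked is given anywhere. The case for acting is that the correction is cheap and that unblinding cannot be undone after dosing.

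**What to change.** In Sections 6.1.3 to 6.1.5, aligned with 6.1.1:

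1. Limit receipt and preparation to the research pharmacist, or a named unblinded preparer, with no role in dosing, adverse-event review or outcome assessment. Remove the wording that lets other research staff receive or prepare drug, make the dispensing sentence in 6.1.5 agree, and reconcile who administers.
2. State that the drug-name label applies to stock only. Give every dispensed syringe an identical coded label in both arms.
3. Cover every dispensed barrel with an opaque sleeve.
4. Release a syringe only after consent and randomisation. Keep the original boxes and per-subject accountability forms (6.2) with the preparer, still open to inspection.
5. Reconcile the volume statements in the Protocol Summary and 6.1.4.

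In Section 10.2.1, send the allocation sequence to the preparer or another holder outside the investigator team, and add to 10.2.3 how a single assignment is obtained when a code break is needed. Without this change the other steps do not secure the blind. Use one term, double or triple, and say who is blinded.

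The cost is protocol and pharmacy wording, plus sleeves and labels for about 40 syringes. The practical burden is that the preparer must be available whenever a patient is randomised. These blinding changes leave dose, visit schedule and sample size as they are.

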6.1.3 PRODUCT STORAGE AND STABILITY

The prepared syringes of Kineret or placebo will be stored in a separate, temperature controlled refrigerator at the investigative site.

Kineret® should be stored in the refrigerator at 2° - 8° C (36° - 46°F). **DO NOT FREEZE OR SHAKE.** Protect from light. Kineret® should not be used after the expiration date unless otherwise notified by the Principal Investigator.

The study drug will be sent to the designated research staff at the University of Kentucky.

Once a subject is identified and consented, the study coordinator will utilize the syringe corresponding to the assigned patient ID to administer the study medication. It has been shown by HPLC analyses, that Kineret is stable for at least 4 hours at ambient temperature and in light in 0.9%NaCl and in a plastic culture vial.³⁸

The refrigerator temperature must be monitored by site personnel on a regular basis and must be recorded on a temperature log sheet or recorded electronically. In the event that the refrigerator's temperature goes outside the $2^{\circ} - 8^{\circ} C (36^{\circ} - 46^{\circ}F)$ range, the Sponsor or designee should be contacted immediately at the telephone number provided in the protocol. Only temperature excursions outside of the acceptable range, per the Sponsor's procedures, are reported as protocol deviations.

6.1.4 PREPARATION

The study drug will be kept in a temperature controlled environment according to the manufacturer's recommendations

Under aseptic clean conditions, a total of 200 mg (1.34 mL) of Kineret® (concentration 100mg/0.67ml) will be injected from 2 sterile original prefilled 100 mg syringes of Kineret into a sterile vial. A sterile graduated 5 mL syringe will then be used to draw 150 mg (1 mL) of Kineret for intraarticular injection into the knee. The medication must be transferred from the original prefilled Kineret syringes as the needles are intended for subcutaneous delivery and are not adequate for intra-articular knee injection. No dilution of the medication will be performed.

For the placebo we will utilize 1 mL of 0.9%NACL sterile saline solution drawn up in the same type of syringe as for the Kineret administration in order to maintain double blinding of the study investigator and patients.

The number of study syringes prepared by the designated research personnel or research pharmacist, per day, will depend on the number of potential enrollees or return patients requiring Kineret® injections that day.

6.1.5 DOSING AND ADMINISTRATION

Study treatment must only be dispensed by a pharmacist or other medically qualified staff. Study treatment is to be dispensed only to subjects enrolled in this study.

Once a subject is identified and consented, the investigator will utilize the syringe corresponding to the assigned patient ID to administer the study medication. It has been shown by HPLC analyses, that Kineret is stable for at least 4 hours at ambient temperature and in light in 0.9%NaCl and in a plastic culture vial.³⁸

- **Group 1** will receive intra-articular injection of Anakinra (Kineret®, IL-1ra; 150mg) 1-28 days after ACL injury.
- **Group 2** will receive intra-articular injection of saline placebo 1-28 days after ACL injury.

6.1.6 ROUTE OF ADMINISTRATION

Intra-articular injection

6.1.7 STARTING DOSE AND DOSE ESCALATION SCHEDULE

The starting dose of Kineret is 150mg. There is no planned dose escalation.

6.1.8 DOSE ADJUSTMENTS/MODIFICATIONS/DELAYS

No dose adjustments or modifications are allowed in this study.

6.1.9 DURATION OF THERAPY

Enrolled participants will receive, based on their randomization, either Kineret or a matching saline placebo within 1-28 days after suffering an ACL injury.

If a participant discontinues the study for any reason prior to 3-month visit, then the collected data will be evaluated but not included in the analysis and a replacement participant will be enrolled in the study.

6.1.10 TRACKING OF DOSE

6.2 STUDY AGENT ACCOUNTABILITY PROCEDURES

It is the responsibility of the Sponsor/Investigator to supervise accurate monitoring of the receipt, storage, dispensing, and accounting of all study drug according to accepted medical and pharmaceutical practice, and should also comply with state and local regulations. The originals of all invoices of study drug shipments must be retained. Accurate, original site records of study

drug inventory and dispensing must be maintained using the forms provided by the Sponsor/Investigator. All disposition records must be made available for inspection by the FDA, DSMB, monitor or designee upon request.

Forms will be provided for the accounting of study drug and for the accounting of study drug for each subject. A reason(s) must be given for any study drug that is not accounted for. Site must keep all used and unused study drug in their original box until the monitor either arranges return to the distribution center or gives instruction on their disposal. If any unused study drug remain at the end of the study, they will be accounted for at the end of the study in the presence of the monitor who will provide instructions on their disposal

7 STUDY PROCEDURES AND SCHEDULE

7.1 STUDY PROCEDURES/EVALUATIONS

7.1.1 STUDY RELATED

Demographic information: Demographic data to be collected at Visit 1 will include height, weight, date of birth, age, gender and race.

Medical and Medication History A detailed past medical history and a list of current medication, to include prescription and over-the-counter medications, will be collected at Visit 1. Assessment of eligibility should include a review of permitted and prohibited medications. Both the medical and medication history will be reviewed with the subject throughout the study for any changes in baseline history.

Physical examination including vital signs, height, weight, BMI. All subjects must have a clinical exam that is consistent with an ACL tear at Visit 1. All subjects will have range of motion (ROM) collected at all visits.

Knee Aspiration: All subjects undergo knee aspiration to dryness at initial encounter Visit 1 (1-28 days after ACL injury), Visit 2 (the time of surgery) and again at Visit 3 (4-14 days post-op). Should a subject be enrolled into the study and choose not to undergo ACL reconstruction, subject will receive treatment according to this protocol but, aspiration at time of surgery will be omitted.

Assessment of Pain and Function –Subject Reported Outcomes – The study will use the standardized subject self-report Knee Injury and Osteoarthritis Outcome Score (KOOS) instrument to assess pain and function in response to the intervention for acute ACL injury. The KOOS is a 100 item instrument that consists of 5 subscales (pain, other symptoms, function in daily living, function in sport and recreation, and knee-related quality of life). The 5 separate subscales provide a complete picture of patients' perceptions of their knee injury and consequences to their daily activities, etc.. KOOS includes the WOMAC osteoarthritis index, which allows for potential comparison with other earlier studies. The KOOS has high test-retest reproducibility (ICC > 0.75). The KOOS subscales for function in sport and recreation and knee-related quality of life have been shown to be the most sensitive subscales pre-operatively and change the most post-operatively (27). The study will supplement the KOOS with self-reported function score assessments from the International Knee Documentation Committee (IKDC) form for evaluation of knee ligament injuries (28) as well as the. Veterans Rand 12-Item (VR-12) health survey and the Patient Acceptable Symptoms State (PASS) question. The questionnaires will be assessed either via an internet based collection software that allows secure data collection

[figure not shown]
through a password coded entry portal or during routine clinical visits using an IPad or paper forms. Paper forms may be used during routine clinical visits or directly mailed to patients.

Specific Pain assessments - Pain coping strategies are important in understanding improvements in pain and psychological disability [46-48]. This study will use a simple Likert pain scale as a pain assessment tools (Figure 3). Pain catastrophizing has been identified as one of the strongest predictors of pain and has been defined as "an individual's tendency to focus on and exaggerate the threat value of painful stimuli and negatively evaluate one's own ability to deal with pain." [49] Not only do individuals who catastrophize, experience more experimental pain (29-31) but also, catastrophizing has been shown to account for 7% to 31% of the variance in pain ratings in varied populations of patients having persistent pain.

MRI analysis: All subjects will undergo MRI examination following Visit 1 and subsequent MRIs will be performed at Visits 5 and 6. Sagittal and axial MRI images will be acquired using a 3.0-T MRI scanner and an 1Tx/15Rx phased array knee coil. Sagittal and axial T1-weighted spin echo images (FSE) will be acquired to allow semi-quantitative analysis at the conclusion of the study. These sequences will be followed by a sagittal high-resolution 3D dual echo steady state (DESS) sequence for cartilage segmentation and a sagittal combined T1p/T2 mapping for the quantification of cartilage composition. The major parameters for the DESS sequences are: FOV = 140 mm, matrix = 384×307×176, resolution = $0.36\times0.45\times0.7$ mm³, time of repetition (TR)/time of echo (TE) = 17.6ms/6.0ms. The T1p/T2 mapping will be acquired using a 3D MAPSS sequence with major parameters: FOV = 140 mm, image matrix = $320\times160\times24$, resolution = $0.44\times0.44\times4$ mm³, time of recovery = 1.5 seconds, bandwidth = 400 Hz/Pixel, TR/TE = 7ms/3ms, time of spin lock (TSLs) = 0, 10, 40, 80 ms for T1p mapping and preparation TEs = 0, 20, 40, 60 ms for T2 mapping. The scan time will be approximately 12 minutes for the combined T1p/T2 mapping. Images will obtained with the knee in full extension.

Images collected at the University of Kentucky will then be transferred digitally to the University of California, San Francisco to be analyzed by [name] and her laboratory. Based on the high resolution DESS images, articular cartilage will be segmented using a spline-based, semiautomatic technique. The T1 ρ map will be created on a voxel-by-voxel basis using established fitting routines. The segmented masks will then be overlaid on the T1 ρ maps after registration between DESS and T1 ρ images, and mean T1 ρ values will be calculated for the entire tibiofemoral cartilage, medial and lateral tibial plateau, medial and lateral femoral condyles, and the patellofemoral compartment will be calculated.

Figure 3. (A) Cartilage subcompartment definition in medial (left) and lateral (right) sides. (B) Meniscal region definition in medial (left) and lateral (right) sides. ¹⁰⁹

